8.4 UNANTICIPATED PROBLEMS

See discussion of UPIRTSO above in 8.3.

Further, there is the possibility that the patient and/or family caregiver will ask clinical questions (e.g. about symptom management) of the study research assistant during a telephone interviews for study-related outcomes assessment. If this occurs, the research assistant will 1. provide the hospice triage phone number to the participant and direct him/her to call about their clinical questions and 2. call the hospice triage phone number directly, inform hospice that the participant had clinical questions, and request a call back to the patient/family caregiver.

9 STATISTICAL CONSIDERATIONS

9.1 STATISTICAL HYPOTHESES

- Primary Endpoint(s): For this exploratory study, the primary endpoints are: acceptability and feasibility of the SPECTORx intervention by hospice stakeholders; feasibility of a brief, standardized, ‘interest in research’ screen upon hospice admission to refer FCG-patient dyads for recruitment; acceptability, burden and completion of FCG assessments (FCG Medication Administration Hassle Scale ³² at baseline, 2 weeks, 4 weeks, 6 weeks, 8 weeks, and monthly).
- Secondary Efficacy Endpoint(s): medication regimen complexity index scores³³ for *chronic daily medications* and prevalence of potentially inappropriate medications (baseline, 2 weeks, 4 weeks, 6 weeks, 8 weeks, and monthly and death), patient quality of life, patient symptom burden

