| | 
• Family caregiver medication burden, as measured by the Family Caregiver Medication Administration Hassle Scale.• Family caregiver satisfaction with care, as determined by likelihood to recommend• Polypharmacy• Potentially inappropriate medication use, as determined by a modified Medication Appropriateness Index• Medication regimen complexity, as measured by the Medication Regimen Complexity Scale• Medication changes• Adverse drug withdrawal events, as measured by a single item single item measure of change in medication since last visit and associated symptom change• Patient Quality of life (QOL), as measured by the McGill QOL Questionnaire (MQOLQ)• Patient Symptoms, as measured by the Edmonton Symptom Assessment System (ESAS)• Performance status, as measured by the Karnofsky Performance Status sale (KPS)• Unanticipated Events (whether study-related or not), as measured by time to first important event, consisting of:
○ admission to a hospital for any reason○ admission to an emergency department for any reason |

- Overall survival, as measured by time-to-death

Endpoints*:

Primary Endpoint: Trial completion

Secondary Endpoints: As described in Secondary Objectives

Study Population:

Eligible participants are adults aged 65 years and older with advanced life-limiting illness with an estimated prognosis of 1-6 months who are prescribed 5 or more medications and their family caregivers.

Phase* or Stage:

Feasibility Trial

**Description of Sites/Facilities
Enrolling Participants:**

Hospice Sites. EOL practices vary regionally.¹³⁻¹⁵ Thus, we are partnering with two large, geographically distinct home hospice agencies to begin exploring the generalizability of SPECTORx nationally. Each agency has multiple offices serving different

local regions within their states. Care Dimensions (Massachusetts) has 2 offices serving 4 counties in Eastern MA, and CNS Home Health & Hospice (Utah) has 10 offices throughout Utah.

Description of Study Intervention/Experimental Manipulation:

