2 INTRODUCTION

2.1 STUDY RATIONALE

Need for a Comprehensive, Patient-Centered, Medication Review and FCG Support Program

A tremendous challenge in home hospice care is ensuring that medication prescribing is appropriately aligned to patients' goals of care and that medications are appropriately managed by FCGs.

There are no intervention studies addressing medication appropriateness in home hospice. Our literature review¹⁶ found one uncontrolled, retrospective study in geriatric palliative care that **reviewed and simplified** regimens by reducing unnecessary drug use by 65% (from 1.7 to 0.6 per patient).¹⁷ Investigators reported that 74% of patients used at least 1 unnecessary medication (defined as drugs with lack of indication, lack of effectiveness, or prolonged duration of therapy). Their study provided "proof of concept" that it is possible to systematically review and simplify medications in geriatric palliative care.¹⁷ However, such studies have focused on geriatrics^{18 19 20 21 22 23} and nursing homes,^{24 25} and not home hospice.

Few studies examine FCG medication management needs.^{14 3 26 27} FCGs have many challenges, including dealing with patients' non-adherence, deciding which medications to give, juggling administration times and monitoring for side effects.^{14 3} Furthermore, patient symptom outcomes depend on appropriate medication administration. (Figure 1) The implication is that high-quality, patient-centered care needs to address *both* medication appropriateness and FCG medication management support.

*Therefore, we propose a novel approach that trains hospice staff to (a) regularly **review, simplify, and align** patients' prescribed medications with their goals of care as their illness progresses,¹⁶ and (b) **support** FCGs' with education that empowers them to understand each medication's use, develop skills for safe administration, and understand when stopping medications may be beneficial.^{3 26}*

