3 OBJECTIVES AND ENDPOINTS

| OBJECTIVES | ENDPOINTS | JUSTIFICATION FOR ENDPOINTS | PUTATIVE MECHANISMS OF ACTION |
|-------------------------------|---|---|-------------------------------------|
| Primary | | | |
| Feasibility and Acceptability | 
 • Intervention Delivery to Hospice Staff • Patient and Family Caregiver Recruitment Goals • Completion of FCGs Assessments • Completion of Patient Assessments • Time for completing FCG assessments • Time for completing Patient Assessments • Yield of FCG Eligibility Criteria • Yield of Patient Eligibility Criteria | 
 • Measurements of Intervention Uptake • Measures of Recruitment Yield • Measure of Outcome Assessment Success | |
| Secondary | | | |
| Efficacy and Safety | 
 • FCG Burden • Medication Regimen Complexity • Patient-Centered Medication Communication | 
 • Primary Outcome for trial • Patient medication burden • Quality of prescribing for patients | |

| OBJECTIVES | ENDPOINTS | JUSTIFICATION FOR ENDPOINTS | PUTATIVE MECHANISMS OF ACTION |
|-----------------------------|--|--|-------------------------------------|
| | 
 Potentially Inappropriate Medications, as measured by modified Medication Appropriateness Index Medication changes Patient QOL, as measured by McGill QOL Questionnaire Patient Symptoms, as measured by Edmonton Symptom Assessment System (ESAS) Overall Survival Suspected Unexpected Serious Adverse Reactions (SUSAR) Drug Related Problems | 
 Key patient outcome Key patient outcome Key patient outcome Assessment of risk for study population Risk assessment for intervention | |
| Tertiary/Exploratory | | | |
| | | | |

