8.2 SAFETY ASSESSMENTS

In accordance with applicable regulatory requirements and principles for the ethical conduct of research, a Safety Officer will be appointed by the NIA to oversee the safety of study participants.

Because the study population has, per the eligibility criteria, a limited expected prognosis of less than one year, death and the preceding associated development of symptoms related to the natural progression of disease are expected. Because the study setting is home hospice, hospitalizations related to the natural progression of disease are expected to be unusual. However, deaths, hospitalizations, and emergency department visits will be monitored.

Because the focus of the trial educational intervention focuses on medication-related management, review and support, medication changes and symptom changes potentially related to drug related problems (DRPs) will be monitored, including potential DRPs present upon study enrollment which, by definition, are not related to the research.

Medication changes will be identified by collecting medication lists every 2 weeks and iteratively identifying changes between lists. DRPs will be monitored by a trained research assistant who will screen the medical record using a Screening Algorithm of Potential Drug Related Problems at *study enrollment and every 2 weeks up to 2 months* for a retrospective chart review, and then monthly up to 6 months. These medical record will be reviewed for new clinical events, symptoms, abnormal lab events and drug levels, new reported drug allergies or drug associated problems identified by clinicians. Secondarily, a trained research assistant will also conduct a screening telephone interview with patients (or their caregiver, if patient is unable to participate) for potential DRPs using a method by Chrischilles³¹ *at 2 weeks and monthly* thereafter.

To ensure that potential DRPs, emergency department visits, hospitalizations and deaths are indeed unrelated to the research, these will be closely monitored by the study's Event Classification Pharmacist (ECP) comprised of a pharmacist using a procedure described below in Section 8.3.

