9.4.3 ANALYSIS OF THE SECONDARY ENDPOINT(S)

A secondary goal of this pilot is to estimate preliminary intervention treatment effect size for a large-scale, R01-funded trial. Comparisons will be made between the baseline and follow-up assessments, both within and across intervention and control sites. Descriptive analyses will establish data distributions for continuous outcomes (e.g. FCG Hassles Scale). We will use linear mixed effects models to account for cluster randomization for continuous outcomes. Clusters are hospice agencies, offices within agencies, clinicians within office, and patients within clinicians/nurses. Even with small samples, we can explore the relationship between change in measures (e.g. # PIMs) and FCG/patient factors. Mixed effects models are robust with small sample sizes and adjust for correlations from repeated measures within individuals and from clustering.

Missing Data. Descriptive analyses will characterize missing data frequency and examine associations with key characteristics (e.g. admitting diagnosis, race). Variables associated with missingness will be included in analyses as covariates to account for possible effects from the missing pattern (missing at random). ³⁶

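### Section 9.1 scores regimen complexity on chronic daily drugs only, so some drug swaps look like simplification, and the inappropriate-drug endpoint has no fixed summary measure

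*Combined protocol and SAP*

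**What the plan says.** **Complexity.** The synopsis (Section 1.1) lists "Medication regimen complexity, as measured by the Medication Regimen Complexity Scale", with no restriction by type of drug, and the Section 3 table also lists regimen complexity without one. Section 9.1 specifies index scores for "chronic daily medications" and does not define the term.

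**Inappropriate drugs.** The synopsis has "Potentially inappropriate medication use, as determined by a modified Medication Appropriateness Index" and Section 3 has "Potentially Inappropriate Medications, as measured by modified Medication Appropriateness Index". Both name an instrument, but neither says whether the result is a count, a score or a yes/no. Section 9.1 names the "prevalence of potentially inappropriate medications" and no instrument. Section 9.4.3 says that "we can explore the relationship between change in measures (e.g. # PIMs) and FCG/patient factors", which points to a count.

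**Related material.** Section 8.2 identifies medication changes by "collecting medication lists every 2 weeks and iteratively identifying changes between lists". Polypharmacy and medication changes are separate secondary outcomes in the synopsis. Section 9.4.3 gives a secondary goal of estimating an effect size for a larger trial, while Section 9.2 states that the pilot lacks power for efficacy.

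**The concern.** Section 4.2 describes the trial as evaluating whether the intervention eases the caregiver's burden of giving medicines. Section 2.2 attributes caregiver stress to a regimen that keeps changing: drugs of doubtful benefit continue while more symptom drugs are added towards the end of life. A complexity score confined to chronic drugs records what is taken away and may miss what is added. It can fall while the caregiver's work stays the same or grows.

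The inappropriate-drug endpoint raises a different problem. With three descriptions in the plan, the summary can be chosen after the data are seen. On one reading of prevalence, a patient who goes from three inappropriate drugs to one shows no change, although reducing such drugs is what the intervention is for.

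At stake is the effect-size estimate to be carried into the later trial. It could be less precise than the data allow, or describe something other than the regimen the caregiver handles.

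**Working it through.** **1. The plan's own figures.** 2 agencies × 2 offices × 15 dyads = 60, or 30 per arm in two offices per arm. The study cited in Section 2.1 reports a fall from 1.7 to 0.6 unnecessary drugs per patient: (1.7 − 0.6)/1.7 = 64.7%, stated as 65%. It also reports 74% of patients with at least one. The plan gives no effect size, standard deviation or intracluster correlation for either medication endpoint.

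**2. Complexity: what a swap does to the score.** Suppose a chronic drug with complexity weight w is stopped and a drug of equal weight is started.

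| Drug started | Chronic-only score | Whole-regimen score |
|---|---|---|
| Non-chronic symptom drug | −w | 0 |
| Another chronic drug | 0 | 0 |

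If the new symptom drug has weight w + 1, the chronic-only score still falls by w while the whole-regimen score rises by 1. The distortion is therefore confined to chronic-to-non-chronic swaps. The documents give nothing from which to estimate how often these occur or their average size.

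**3. Inappropriate drugs: yes/no against count.** Assume that prevalence means at least one such drug. For means m1, m2 with variances v1, v2, and proportions p1, p2 with at least one:

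- information in the count: (m1 − m2)² / (v1 + v2)
- information in the yes/no: (p1 − p2)² / [p1(1 − p1) + p2(1 − p2)]
- loss = 1 − (yes/no) / (count)

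The count distribution is an assumption. For a Poisson, v = m and p = 1 − exp(−m). At mean 1.7 this gives p = 0.817, above the cited 74%. A negative binomial with mean 1.7 and p = 0.74 needs size k = 3.0, with v = m + m²/k.

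Worked case, Poisson, 1.7 to 0.6: the count gives 1.1²/2.3 = 0.526. The yes/no, with p = 0.817 and 0.451, gives 0.134/0.397 = 0.338. The ratio is 0.64, a loss of 36%.

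| Contrast | Loss, Poisson | Loss, negative binomial |
|---|---|---|
| 1.7 to 0.6 | 0.358 | 0.349 |
| 1.7 to 1.0 | 0.505 | 0.511 |
| 1.7 to 1.2 | 0.547 | 0.554 |
| 1.7 to 1.4 | 0.580 | 0.585 |

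The loss is thus about 35% for the cited fall and about 58% for a small effect. A Poisson baseline of 1.35 (the mean that gives 74%) with the same relative fall, to 0.47, gives 26%. A very small effect at mean 1.7 gives about 62%. A baseline above 1.7 would raise the loss further: a very small Poisson effect at mean 2.0 gives 69%.

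**4. The same comparison in patients.** With the negative binomial, two-sided 5% and 80% power (both assumed) and no clustering, the 1.7 to 0.6 contrast needs 22 per arm on the count and 37 on the yes/no. At 30 per arm, power is 91% and 72%. These figures only illustrate the relative loss, since the pilot is not powered for efficacy.

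**The case against.** A reader might infer that Section 9.1 narrows both endpoints against the synopsis and so discards 35-58% of the information in each. The documents do not support that. The synopsis and Section 3 name an instrument for inappropriate drugs but no summary measure, so a prevalence judged by the modified index would contradict neither. The count that serves as comparator appears only in Section 9.4.3, and no loss figure can be derived for complexity.

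The percentage also depends on one reading. If prevalence means the share of drugs that are inappropriate, or if the Section 9.4.3 count is what gets analysed, this loss does not arise. Section 9.4.3 specifies mixed models for continuous outcomes and gives none for a yes/no outcome, which favours the count. The inputs come from an uncontrolled, retrospective study outside home hospice, whose definition of unnecessary is not the modified index, and its before-after change is treated here as two independent arms. These limits stand. They make the figure conditional, but they do not settle which measure is the endpoint.

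The chronic-only scope may be deliberate: the intervention looks for drugs that can be stopped or tapered, while symptom drugs rise in any case. That justifies keeping the score, but not reporting it alone as regimen complexity. Polypharmacy, medication changes and the change listings in Section 9.4.6 would partly reveal added drugs, and the Hassle Scale measures caregiver burden directly. None of the medication outcomes among these measures complexity, so the gap is reduced but remains.

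**Conclusion.** The point holds in two separate parts. First, Section 9.1 restricts complexity to an undefined class of drugs while the synopsis and Section 3 do not, and the restricted score counts replacement of a chronic drug by a non-chronic one as simplification. Section 2.2 makes that pattern likely, but its size cannot be estimated from the documents. Whether scheduled symptom drugs fall inside the class is also unknown.

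Second, the summary measure for inappropriate drugs is inconsistent. If the yes/no reading is used, the loss against the count is roughly 35-58% at the cited baseline, and about 26-62% over the baselines of 1.35 to 1.7 examined. This rests on assumed count distributions and borrowed figures, and ignores clustering and repeated measures.

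It would be wrong to conclude that every drug swap is scored as simplification, since a swap between chronic drugs of equal weight is not, or that data are lost, since the lists are collected in any case. Because these are secondary endpoints in a feasibility pilot, severity is minor. The gain is a more precise and better-directed effect-size estimate for the later trial.

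**What to change.** Reconcile the synopsis and Sections 3, 9.1 and 9.4.3 as follows.

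- **Inappropriate drugs.** In Section 9.1, define the endpoint as the number of inappropriate drugs per patient at each visit, judged by the modified index and analysed as in Section 9.4.3. Keep prevalence as a supporting summary and state its denominator (patients or drugs).
- **Complexity.** Define chronic daily, stating whether scheduled symptom drugs are included. Report the complexity index by arm for the full regimen alongside the chronic-only score.

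Both use the medication lists already collected and keep the plan's existing measures. The cost is a change of wording plus extra scoring. The downside is that as-needed and symptom drugs must also be coded for the whole-regimen score.

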9.2 SAMPLE SIZE DETERMINATION

Sample Size Justification. In this exploratory study, we chose a sample size sufficient to enable a decision about feasibility.³⁴ This sample size is larger than many pilot palliative care trials and sufficient to determine acceptability in each of the two hospice agencies.³⁵ This sample size is also attainable. Target enrollment is 30 FCG-dyads at each hospice agency who, combined, have over 400 admissions a month. We lack power to establish efficacy for the intervention on outcomes.

9.3 POPULATIONS FOR ANALYSES

While we aim to enroll dyads of family caregivers and patients, the population for analysis include family caregiver outcome separate from patient outcomes.

9.4 STATISTICAL ANALYSES

9.4.1 GENERAL APPROACH

9.4.2 ANALYSIS OF THE PRIMARY ENDPOINT(S)

Feasibility and Acceptability. We will use descriptive statistics to analyze *quantitative feasibility outcomes*. We will calculate the mean number of eligible patient-FCG dyads screened and enrolled per week, accrual, retention, and training completion. We will use Chi-square (for comparisons of rates and

proportions) and t-tests (for mean comparisons) to explore differences by site and participant characteristics, including sex.

9.4.3 ANALYSIS OF THE SECONDARY ENDPOINT(S)

A secondary goal of this pilot is to estimate preliminary intervention treatment effect size for a large-scale, R01-funded trial. Comparisons will be made between the baseline and follow-up assessments, both within and across intervention and control sites. Descriptive analyses will establish data distributions for continuous outcomes (e.g. FCG Hassles Scale). We will use linear mixed effects models to account for cluster randomization for continuous outcomes. Clusters are hospice agencies, offices within agencies, clinicians within office, and patients within clinicians/nurses. Even with small samples, we can explore the relationship between change in measures (e.g. # PIMs) and FCG/patient factors. Mixed effects models are robust with small sample sizes and adjust for correlations from repeated measures within individuals and from clustering.

Missing Data. Descriptive analyses will characterize missing data frequency and examine associations with key characteristics (e.g. admitting diagnosis, race). Variables associated with missingness will be included in analyses as covariates to account for possible effects from the missing pattern (missing at random). ³⁶

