4 STUDY DESIGN

4.1 OVERALL DESIGN

A pilot, single-blinded, cluster randomized, pragmatic trial of the SPECTORx intervention.

We will compare outcomes within and across 2 large, multi-office, hospice agencies from Utah and Massachusetts. Within each hospice agency, we will randomize 1 office to intervention and 1 office to attention control. Target enrollment is 30 FCG-patient dyads per agency (n=15 intervention, n=15 control), for a total trial target of n=60 FCG-dyads of patients aged ≥ 65 years, with an estimated life expectancy of >1 month, and polypharmacy (defined as ≥ 5 regularly scheduled daily medications).

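### Section 9.4.3 does not say which comparison supplies the effect size for the later trial, and states no adjustment for the baseline outcome value

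*Combined protocol and SAP*

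**What the plan says.** All references are to the combined protocol and SAP.

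- **Purpose.** Section 9.4.3 opens: "A secondary goal of this pilot is to estimate preliminary intervention treatment effect size for a large-scale, R01-funded trial".
- **Comparisons.** The next sentence reads: "Comparisons will be made between the baseline and follow-up assessments, both within and across intervention and control sites". Neither sentence says which comparison gives the effect size.
- **Model.** "We will use linear mixed effects models to account for cluster randomization for continuous outcomes". The section adds that such models "adjust for correlations from repeated measures within individuals and from clustering". It gives no model equation and no arm-by-time term.
- **Cluster levels.** "Clusters are hospice agencies, offices within agencies, clinicians within office, and patients within clinicians/nurses".
- **Covariates.** The only ones named are under missing data: "Variables associated with missingness will be included in analyses as covariates". The baseline value of the outcome is not mentioned.
- **Randomisation.** Section 4.1: "Within each hospice agency, we will randomize 1 office to intervention and 1 office to attention control". That gives two agencies, four offices and two offices per arm.
- **Baseline data.** The schedule in section 1.3 has the Hassle Scale, medications, KPS, MQOLQ and ESAS at enrolment and at follow-up.
- **Natural course.** Section 8.2 says that "death and the preceding associated development of symptoms related to the natural progression of disease are expected". Section 2.2 says that end-of-life symptom drugs are added over time.

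Sections 9.4.1 and 9.4.9 are headings without text, so they do not fill the gaps.

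**The concern.** An effect size carried into a larger trial should estimate what the intervention adds. Change from baseline in the intervention offices alone does not, because symptoms, drug counts and caregiver burden can move in patients near death whatever the staff were taught. If a within-arm change is read as the effect, the later trial may be sized on natural course. The error can run either way: drift toward improvement would mimic a benefit, and drift toward worsening would hide one.

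Two further gaps concern the between-arm contrast. A baseline is collected for the main continuous outcomes, but no adjustment for it is stated, so precision that costs nothing is left to later choice. Agency is the stratum within which offices are randomised and has only two levels, yet it is listed as a cluster level. Two levels leave a single degree of freedom for a variance component.

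**Working it through.** **Plan's own figure.** Section 9.4.3 gives no power, SD, ICC or alpha to reproduce. The sample size is consistent: 2 agencies × 2 offices × 15 dyads = 60, or 30 per arm.

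**Assumptions.** The documents give neither the drift nor the baseline/follow-up correlation ρ. I use drifts of 0.2, 0.3 and 0.5 SD, equal in both arms, and ρ of 0.3, 0.5 and 0.7.

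**1. What a within-arm test would show with no intervention effect.** The SD of change is √(2(1−ρ)). For a two-sided 5% paired t-test the non-centrality is drift × √n / √(2(1−ρ)). With n = 30, the chance of a significant change in one arm is:

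| Drift (SD) | ρ = 0.3 | ρ = 0.5 | ρ = 0.7 |
|---|---|---|---|
| 0.2 | 15% | 19% | 28% |
| 0.3 | 27% | 36% | 54% |
| 0.5 | 61% | 75% | 93% |

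With 20 per arm assessed, the rates at ρ = 0.5 are 14%, 25% and 57%.

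The misleading pattern is significance in the intervention arm and not in control. With p the one-arm rate, its chance is p(1−p). At ρ = 0.5 and n = 30:

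- drift 0.3: 0.355 × 0.645 = 0.23
- drift 0.4: 0.563 × 0.437 = 0.25
- drift 0.5: 0.754 × 0.246 = 0.19

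These figures count a change in the direction of the drift, whichever that is. If the drift is toward worsening, a significant within-arm improvement with no effect has probability below 2.5%. The risk is then the reverse: a true benefit of 0.3 SD against a worsening of 0.3 SD gives an expected within-arm change of 0.3 − 0.3 = 0, while the between-arm difference is still 0.3 SD.

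**2. What baseline adjustment gains in the between-arm contrast.** In units of the follow-up variance, the relative variance is 1 for follow-up only, 2(1−ρ) for change scores and 1−ρ² with baseline as a covariate. SE = √(relative variance × 2/30), ignoring office variance.

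| ρ | Follow-up only: SE | Change: variance, SE | Adjusted: variance, SE | Adjusted ÷ change | Cut against follow-up only |
|---|---|---|---|---|---|
| 0.3 | 0.258 | 1.40, 0.306 | 0.91, 0.246 | 65% | 9% |
| 0.5 | 0.258 | 1.00, 0.258 | 0.75, 0.224 | 75% | 25% |
| 0.7 | 0.258 | 0.60, 0.200 | 0.51, 0.184 | 85% | 49% |

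**3. Agency fixed or random.** In 300 simulated trials of 2 × 2 × 15 dyads (ρ = 0.5, agency variance 0.05, office variance 0.02, both models baseline-adjusted and without an office term), the arm estimate differed by 0.003 SD on average and by at most 0.022. The mean SE was 0.224 with agency fixed and 0.223 with agency random. This is as expected, because arms are balanced inside each agency.

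**4. The limit set by four offices.** Four office means less two arm means leave 2 degrees of freedom for the arm effect (critical t 4.30). Allowing for agency leaves 1 (critical t 12.71). At ρ = 0.5 and with no office variance at all, the 95% half-width is 4.30 × 0.224 = 0.96 SD or 12.71 × 0.224 = 2.85 SD.

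**The case against.** The strongest reply is that the sentence on comparisons already contains the remedy. It plans comparisons across arms as well as within them, and an across-arm comparison of change cancels a shared drift. The section names no within-arm test, p-value or alpha; its named method is a repeated-measures mixed model. It calls the effect size preliminary, and section 9.2 says the trial lacks power for efficacy. All of this stands, and it limits the point to a gap in specification.

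A reader might infer three stronger things that the documents do not support:

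- **That natural course will probably be reported as an intervention effect.** The text never says that the effect size comes from within-arm change. Even if within-arm tests were run, the misleading pattern has a chance of about 19% to 25% at ρ = 0.5 and drifts of 0.3 to 0.5 SD. The course the protocol describes is worsening, which would more often hide a benefit than mimic one.
- **That listing agency as a cluster lets natural course pass as effect.** It cannot, because arms are compared inside each agency. The section does not use the word random for agency either; that is an inference from its place among the clusters.
- **That the baseline goes unused.** It enters through change and through repeated measures. What is missing is a stated adjustment of the between-arm contrast.

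Adjusting for one baseline outcome also does not balance two offices per arm on other characteristics.

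**Conclusion.** The point holds as a specification gap of low severity. Section 9.4.3 leaves open which comparison gives the effect size, does not mark within-arm change as descriptive, and states no baseline-outcome adjustment.

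The precision gain is real at participant level: variance falls by 15% to 35% against change scores and by 9% to 49% against follow-up only, for ρ from 0.7 down to 0.3 in the first case and from 0.3 up to 0.7 in the second. It rests on assumed correlations and excludes office variance. It does not rescue the estimate: with 1 or 2 degrees of freedom for the arm effect, the interval is very wide under any model. Treating agency as fixed corrects the specification and has little numerical effect on the estimate or its model-based SE in this balanced design.

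**What to change.** Amend section 9.4.3 as follows.

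1. State that the effect size is taken only from the between-arm difference at follow-up in the mixed model, with the participant's own baseline value of that outcome as a covariate, and is reported with a confidence interval.
2. State that within-arm change from baseline is reported descriptively, without tests, and is not used as an effect size.
3. Enter agency as a fixed effect, because it is the randomisation stratum and has two levels, and keep office as the cluster level. Base the interval on the number of offices, and say that it will be very wide.

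The cost is analysis-plan wording only. The baseline values are already in the schedule of activities, and no assessment, visit or participant is added.
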